8.3 ANALYSIS POPULATIONS

8.3.1 Intention-to-treat population (ITT)

ITT population will include all randomised patients analysed in the groups to which they were randomised to, regardless of whether they received or adhered to the allocated intervention.

8.3.2 Per-protocol population (PP)

PP population will include all patients who completed the study (Days 0-7) without reported protocol violations.

8.3.3 Safety population

The safety population is the analysis population based on which AEs will be summarised and reported. This population will include all randomised patients who received at least 1 dose of study treatment. In this population, patients will be analysed according to the treatment they actually received, regardless of the treatment they were randomised to.

9 QUALITY CONTROL AND QUALITY ASSURANCE

9.1 DATA HANDLING AND RECORD KEEPING

All study data will be entered using a validated electronic Case Report Form (eCRF) ENT02UK Protocol v.1.4 11/06/2018 system, where the participants will be identified by a study-specific participant number. Data recorded in the eCRFs will not contain any patient identifying information.

Data collection is the responsibility of the clinical trial staff at the site under the supervision of the site PI. The PI is responsible for ensuring the accuracy, completeness, legibility, and timeliness of the data reported. All source documents should be completed in a neat, legible manner to ensure accurate interpretation of data. Data reported in the eCRF derived from source documents, i.e. medical records and the patient diaries, should be consistent with the source documents or the discrepancies should be explained and captured in a progress note and maintained in the participant's official electronic study record.

Study documents should be retained at site for a minimum of 2 years after the End of Trial. No records will be destroyed without the written consent of the Sponsor, if applicable. It is the responsibility of the Sponsor to inform the Investigator when these documents no longer need to be retained.

9.2 DATA QUALITY

The study will be conducted in accordance with the current approved protocol, ICH GCP, relevant regulations and standard operating procedures. Regular monitoring will be performed according to ICH GCP and a study-specific Trial Monitoring Plan. Data will be evaluated for compliance with the protocol and accuracy in relation to source documents.

Following written standard operating procedures, the monitors will verify that the clinical trial is conducted and data are generated, documented and reported in compliance with the protocol, GCP and the applicable regulatory requirements.

9.3 PROTOCOL DEVIATIONS AND VIOLATIONS

A protocol deviation is any noncompliance with the clinical trial protocol or GCP. The noncompliance may be either on the part of the participant, the investigator, or the study site staff.

Protocol violations are significant deviations that reduce the quality or completeness of the data, make the Informed Consent Form inaccurate, or impact a subject's safety, rights, or welfare (16).

Examples of protocol violations relevant to this study may include the following:

- 1. Inadequate or delinquent informed consent
- 2. Inclusion/exclusion criteria not met
- 3. Unreported SAEs
- 4. Use of any prohibited medication (i.e. any antidiarrhoeal medications)

- Inadequate completion of the patient diary (i.e. data missing systematically, diary missing entirely for one or more days, any data entry issues that compromise the verification of primary outcome data against the source)
- 6. Materially inadequate record keeping
- 7. Intentional deviation from the protocol, GCP, or regulations by study personnel
- 8. Subject repeated non-compliance with study requirements, including not using any Enterosgel®, if randomised to Enterosgel group

Examples of protocol deviations relevant to this study may include the following:

- 1. Stool sample not taken, or taken after Day 0
- 2. One or more calls missed
- Infrequent missing data in patient diary (however, any missing data affecting the interpretation of the primary outcome would be recorded as a protocol violation)

All deviations/violations must be addressed in study source documents and reported to the Sponsor and Research Ethics Committee (REC) and/or local authorities as per their guidelines. The site PI/study staff is responsible for knowing and adhering to these requirements. As a result of deviations and violations, corrective actions are to be developed by the Sponsor and/or site as appropriate and implemented promptly.

Patients with protocol violations will be excluded from the PP population.

10 ETHICAL CONSIDERATIONS

10.1 GENERAL CONSIDERATIONS

This study will be conducted in accordance with the recommendations guiding physicians in biomedical research involving human subjects adopted by the 18th World Medical Assembly of Helsinki (1964), revised at Tokyo (1975), Venice (1983), Hong-Kong (1989), Somerset West (1996), Edinburgh (2000) and Seoul (2008), including the Notes of clarification made by the World Medical Assembly of Washington (2002), Tokyo (2004), Seoul (2008) and Fortaleza (2013) as well as in compliance with ICH GCP guidelines.

The Investigators and the Sponsor are responsible for ensuring that all activities in relation to this study are conducted in accordance with the protocol, GCP guidelines and any other relevant regulations. All the personnel involved in the

study will be fully informed about the nature of the study and will be subject to protocol procedures concerning their duties in the study.

The protocol, PIS, informed consent form(s), recruitment materials, and all participant materials will be submitted to the REC for review and approval. Approval of all relevant documents must be obtained before any participant is enrolled. Any substantial amendments to the protocol or other study documents will require review and approval by the REC before the changes can be implemented to the study.

10.2 PATIENT CONSENT

The participant will sign the informed consent document prior to any procedures being done specifically for the study. Participants will have the opportunity to carefully review the study information and ask questions prior to providing consent. A copy of the informed consent document will be given to the participants for their records.

Participants may withdraw consent at any time throughout the course of the trial. The rights and welfare of the participants will be protected by emphasising to them that the quality of their medical care will not be adversely affected if they decline to participate in this study.

10.3 PATIENT CONFIDENTIALITY

The Investigators affirm and uphold the principle of the participant's right to privacy and that they shall comply with applicable privacy laws. Anonymity of the participants shall be guaranteed when presenting the data at scientific meetings or publishing them in scientific journals. Individual subject medical information obtained as a result of this study is considered confidential and disclosure to third parties is prohibited. Subject confidentiality will be further ensured by utilising subject identification code numbers to correspond to treatment data in the computer files.

For data verification purposes, authorised representatives of the Sponsor, a competent authority, or REC may require direct access to parts of the medical records relevant to the study, including participants' medical history.

10.4 PAYMENTS TO PATIENTS

Patients will receive £20 to cover travel expenses for delivering the stool sample.

11 PUBLICATION AND DISSEMINATION

This study has been registered with International Standard Randomised Controlled Trial Number (ISRCTN) (ISRCTN20758708).

Study results will be submitted for presentation(s) at gastroenterology conference(s) and for publication in international peer-reviewed scientific journal(s).

The Investigators will be involved in reviewing drafts of the manuscripts, abstracts, press releases and any other publications arising from the study. Authors will acknowledge that the study was funded by Enteromed Ltd. Authorship will be determined in accordance with the ICMJE guidelines and other contributors will be acknowledged.

Results will be submitted for inclusion into the NICE guidance if valuable for NHS.

12 FINANCE AND INSURANCE

This study is funded by Bioline Products s.r.o., who is the manufacturer of Enterosgel®. The study Sponsor, EnteroMed Ltd, is the exclusive distributor of Enterosgel® in the UK and holds a Product Liability Insurance for legal liabilities arising from the use of Enterosgel® in the UK.

NHS bodies are legally liable for the negligent acts and omissions of their employees. If a patient is harmed whilst taking part in a clinical study as a result of negligence on the part of a member of the study team this liability cover would apply.

13 CONFLICTS OF INTEREST

The Sponsor and coordinator of this study (EnteroMed Ltd) is the exclusive distributor of Enterosgel® in the UK.

The Chief Investigator has no conflicts of interest.

15 APPENDICES

APPENDIX A: ENTEROSGEL® STUDY USE INSTRUCTIONS

Randomised, multi-centre study to assess efficacy, tolerability and safety of Enterosgel® in treatment of acute diarrhoea in adults

Enterosgel® use instructions for research participants

IMPORTANT:

- Stop taking Enterosgel® if you did not have any bowel movements for 2 days at any stage of the study
- Mix every dose of Enterosgel® in 100-200 ml of room temperature water
- Please leave at least 1 hour between taking Enterosgel® and any other medication or meals

Day 0 (today):

First dose (as soon as possible): 2 tablespoons or 2 sachets of Enterosgel®

After the first dose: 1 tablespoon or 1 sachet of Enterosgel® after every bowel movement up to a total of 6 times and at least 3 times a day

Day 1:

If you have loose stool more than once a day:

1 tablespoon or 1 sachet of Enterosgel® after every bowel movement up to a total of 6 times and at least 3 times a day

If you don't have loose stool or have it just once a day:

1 tablespoon or 1 sachet of Enterosgel® 3 times a day

Days 2, 3, 4 and 5:

If you have loose stool more than once a day:

1 tablespoon or 1 sachet of Enterosgel® 3 times a day

If you don't have loose stool or have it just once a day:

1 tablespoon or 1 sachet of Enterosgel® 1-2 times a day

Days 6 and 7:

If you have loose stool more than once a day:

1 tablespoon or 1 sachet of Enterosgel® 3 times a day

If you don't have loose stool or have it just once a day:

Stop taking Enterosgel®

ENT02UK

Enterosgel® use instructions v.1.0

12/10/2016

APPENDIX B: ENTEROSGEL® STANDARD PATIENT INFORMATION LEAFLET

Patient Information Leaflet.

Please read this Leaflet carefully before you start taking Enterosgel®. Keep this Leaflet. You may need to read it again. If you have any further questions, ask your doctor or pharmacist.

1. What is Enterosgel® and what it is used for?

Enterosgel^a is an innovative intestinal adsorbent developed for binding toxins, allergens, pathogens and other harmful substances in the gastrointestinal tract, to help remove them from the body.

ENTEROSGEL® is an ancillary treatment for diarrhoea and is used in children and adults in the following conditions:

- ✓ Acute diarrhoea (Gastroenteritis).
 ✓ Allergies with gastrointestinal symptoms (Not used for treatment of anaphylactic shock)
- ✓ Irritable Bowel Syndrome with diarrhoea (IBS-D).

2. How should I take Enterosgel®

Enterosgel® in a tube:

Enterosgel® in a sachet:

Age	Dosage	How Often	
Child 1–6	1 teaspoon or 5g	3 times	
years old	or 1/3 of sachet	a day	
Child 7–14	2 teaspoons or 10g	3 times a day	
years old	or 1/2 of sachet	a day	
15+	1–1,5 tablespoon or 15 to 22.5g	3 times	
and adults	1–1,5 sachet	a day	

- For babies and children 1 to 3 years old Enterosgel® can be used under advice of a doctor. Enterosgel® should be administered orally 1–2 hours before or after a meal. When this product is taken it is recommended to wash it down with sufficient quantity of water or dilute the dose in water of room temperature prior to its administration (in 200 ml of water for adults and children 7 and over, 50-100 ml of water for children aged 1–6).
- Enterosgel® may affect the absorption of some medicines that are administered orally – use Enterosgel® 1–2 hours before or after taking medication. If you are taking any medication, you may also consult with your doctor or pharmacist regarding taking Enterosgel®.
- If there is blood in the stools, signs of dehydration or symptoms have continued for more than 2 days, seek medical advice especially in the case of children.

3. Contraindications

Intestinal atony (severe constipation due to bowel obstruction). Intolerance, based on prior use of ENTEROSGEL*.

4. Pregnancy and breastfeeding

Enterosgel® can be taken during pregnancy and breastfeeding. It is recommended to speak to your GP or midwife if you are unwell during pregnancy.

5. Additional information

Composition: polymethylsiloxane polyhydrate (methylsilicic acid hydrogel) – 70%, water purified – 30%.

Enterosgel is free from preservatives, colouring, gluten, fat, sugar, lactose, flavours and sweeteners.

Packaging:

Oral suspension in tube 225g, tube 90g, sachet 15g (10 sachets per package).

Note:

Please, shake the tube or a sachet well before use. When squeezing Enterosgel* out of the tube or a sachet some amount of liquid may appear.

Storage parameters:

Store at temperatures of 4–25°C. Keep out of the reach and sight of children.

Avoid drying out after opening the package. Do not freeze! Use the tube within 30 days after opening. Use a sachet within 24 hours after opening.

Shelf life:

Three years. Not to be used beyond the expiry date indicated on the package.

What to do if the package is damaged:

Do not use the product if the package is damaged.

Date of last revision: 10 February 2016

Useful information on the mechanism of action of Enterosgel®

The gastrointestinal tract plays an essential role in maintaining good health: delivers necessary nutrients; serves as one of the main routes of elimination of harmful substances and toxins; performs barrier and immune functions.

Causes of diseases and symptoms

Acute exposure of the gastrointestinal tract to pathogens, toxins, allergens, and xenobiotics (pesticides, radionuclides, salts of heavy metals, etc.) results in development of gastrointestinal infections, intoxication and allergic reactions. Vital bodily functions are associated with the production of harmful and toxic metabolites. Part of them having reached the gut are usually eliminated from the body with faeces, but some of harmful substances may be reabsorbed into the bloodstream again and transported back to the liver, remaining in the enterohepatic circulation. The most common symptoms of acute intoxication include a feeling of general malaise, headache, nausea, vomiting, diarrhoea, allergic manifestations, and elevated body temperature.

What can be done?

Detoxification – elimination of toxins and pathogens from the gastrointestinal tract – is an important step towards achieving recovery, optimal health and longevity. The active substance of Enterosgel® is an organosilicon compound -polymethylsiloxane polyhydrate. It has a porous structure, and a gel-like consistency. This allows Enterosgel® to bind harmful substances to its surface and remove them from the body. Detoxification leads to improvement of general well-being, normalization of digestion and augmentation of resistance to infection, and helps the body work under optimal conditions.

Bioline Products s.r.o., [name], Czech Republic tel./fax: [name] e-mail: [contact] www.enterosgel.eu

Exclusive Distributor in the UK:
EnteroMed Ltd

[name]
[contact]
www.enterosgel.co.uk

${\bf Explanation\ of\ graphic\ symbols\ on\ package:}$

Certified medical device

Disposable packaging. Dispose of used packaging in appropriate waste receptacle.

Packaging can be recycled

A fee for the national packaging management system has been paid for this packaging.

ZP/EN/NEW/2

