4 STUDY PARTICIPANTS

4.1 INCLUSION CRITERIA

- 1. Informed consent
- 2. Patient-reported episode of acute diarrhoea defined as at least 3 watery stools within the last 48 hours
- 3. Aged 18 to 70

- 4. Willing and able to comply with the study protocol and evaluation(s) specified in the protocol
- 5. Considered suitable to take part in the study by the consenting nurse/GP (based on medical history and physical examination)

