4.2 EXCLUSION CRITERIA

- 1. History of intestinal atony (severe constipation due to bowel obstruction)
- 2. Blood in stools
- 3. Any underlying condition that could cause chronic diarrhoea (such as gastroduodenal ulcer, ulcerative colitis, or Crohn's disease)
- 4. Patients with known cancer of any localisation
- 5. Use of any clinical trial investigational medication within the last 30 days before screening visit
- 6. Use of antibiotics since the onset of current diarrhoea episode
- 7. Pregnancy*
- 8. A history of clinically significant allergic reactions
- 9. Any underlying condition that could affect the patient's participation in this study or the results of this study in Investigator's opinion
- * Patient-reported; last menstrual period date will be recorded.

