6 STUDY SCHEDULE AND PROCEDURES

Patients will complete 1 visit at their GP practice with 7 follow-up phone calls after the visit. The patients will not be invited for visits outside their standard of care regime. The schedule of visits/calls, and the procedures conducted and data collected at each visit/call are presented in **Table 1**. A +/- 2-day deviation is allowed for the Day 7 follow-up call.

Table 1. Schedule of procedures and data collection.

Procedure	Day 0 (Screening Visit)	Days 1- 7 (Follow-up calls)	End of study
Patient screening and consent	Х		
Demographic information and relevant medical history, symptoms and medication	x		
Randomisation	X		
Prescription for ORS (all patients) and provision of Enterosgel® (Interventional group)	Х		
Stool sample	X		
Other symptoms (vomiting, abdominal pain, nausea, fever etc)*	х	х	
Body temperature*		x	
Stool frequency and form*		х	
Medication use*		х	
Adverse Events*	 	x	
Returning of the diaries			х

^{*}Recorded by the patient in a patient diary from Day 0 (after randomisation) until end of Day 7 (**Appendix C**)

6.1.1 Day 0

On the Day 0 appointment, the patient's eligibility to take part in the study will be confirmed by the GP and written informed consent will be obtained by the GP or nurse before any study procedures take place. Screening will include a physical examination by the GP/nurse to ensure the patient is suitable to take part in the study (including measurement of body temperature, pulse and blood pressure).

The following information is then recorded in the eCRF:

- 1. Demographic information (age, gender, ethnicity)
- 2. Relevant medical history:
 - a) date of onset of symptoms (diarrhoea, vomiting, nausea, abdominal pain, fever etc.)
 - b) contact with suspected infection
 - c) details of travel
 - d) details of possible food poisoning
 - e) any antidiarrheal medication taken during the current episode

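### Section 4.2 turns one of the device leaflet's two contraindications into an exclusion but omits the other, intolerance on earlier use of Enterosgel

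*Protocol*

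**What the plan says.** Part 3 of the leaflet in Appendix B of the Protocol lists two contraindications. One is intestinal atony; the other is "Intolerance, based on prior use of ENTEROSGEL".

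Section 4.2 has nine exclusion criteria. The first is "History of intestinal atony (severe constipation due to bowel obstruction", which matches the leaflet's first contraindication almost word for word. The eighth is "A history of clinically significant allergic reactions". The ninth leaves it to the investigator to exclude a patient with an underlying condition that could affect participation or results. None of the nine mentions Enterosgel, earlier use of it, or intolerance.

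Section 4.1 adds a general screen as inclusion criterion 5: "Considered suitable to take part in the study by the consenting nurse/GP (based on medical history and physical examination". Table 1 in Section 6 schedules "Demographic information and relevant medical history, symptoms and medication" for the Day 0 visit. Section 9.3 gives "Inclusion/exclusion criteria not met" as an example of a protocol violation.

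**The concern.** Section 3.1 presents the trial as a post-marketing study of a device used for its intended purpose, and tolerability and safety are a secondary objective in Section 2.2. In such a trial one expects every labelled contraindication to appear among the exclusions, so that whoever confirms eligibility is prompted to ask about each. Here one of the two appears and the other does not, and no reason is given.

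At stake is whether a patient for whom the label advises against the gel could be randomised because nobody asked. Enterosgel is sold over the counter in UK pharmacies and health stores (Section 5.2.1), so earlier use need not be in the GP record. Recruitment may run through local pharmacies and the sponsor's own website and social media (Section 4.3), and the sponsor is the exclusive UK distributor (Section 12). These routes could plausibly reach former users, though the Protocol does not say how many there are.

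**Working it through.** No formula applies and the Protocol states no figure on this point. The check sets the leaflet beside the eligibility criteria.

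**Step 1. Leaflet against Section 4.2**

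| Contraindication in Appendix B | Matching exclusion in Section 4.2 |
|---|---|
| Intestinal atony | Exclusion 1, in nearly the same words |
| Intolerance on earlier use of the product | None of the nine |

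One of two contraindications has an explicit exclusion.

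**Step 2. Do the neighbouring criteria cover the second contraindication?**

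- *Exclusion 8* is about allergic reactions. It would cover a clinically significant allergic response to the gel. It does not cover a patient who, for example, could not tolerate the gel for gastrointestinal reasons.
- *Exclusion 9* requires an underlying condition. Having tolerated a product badly in the past is not clearly a condition, so the reading is arguable.
- *Inclusion 5* does cover it. A nurse or GP who knows of the intolerance should judge the patient unsuitable. The criterion rests on history and examination, and an examination cannot show past intolerance of a product. It works only if the history is volunteered or elicited.

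**Step 3. Is there another prompt in the text shown?** The study instructions in Appendix A go to patients allocated to the gel, after randomisation, and do not mention intolerance. The leaflet is cited in the device description (Section 5.2.1), but the Protocol does not say that it is used at screening.

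**Step 4. Is Section 4.2 deliberately limited to the label?** No. It excludes pregnancy, which the leaflet and Section 5.2.1 allow. It is stricter than the label there and silent on a labelled contraindication here.

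**Result.** Known non-allergic intolerance is screened only through the general judgement in inclusion 5.

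**The case against.** The best reply is that the patient would be kept out anyway. Inclusion 5 is an eligibility criterion like any other, so enrolling someone judged unsuitable is already a violation under Section 9.3. Inclusion 4 asks for willingness and ability to comply, which a person who knows that the gel disagrees with them would struggle to meet. The patient is the one most likely to know, and Section 4.3 gives them an information sheet and time to consider it before consent. That sheet and the eCRF itself are not shown and may ask the question. Section 4.2 does not claim to reproduce the leaflet, and nothing in the Protocol permits enrolling an intolerant patient.

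Most of this stands. A reader might infer that contraindicated patients would have to be enrolled, or that enrolling one knowingly would breach no criterion. Neither follows, because inclusion 5 applies and carries the same force as the listed exclusions.

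A reader might also infer from Section 6.1.1 that earlier use is never asked about. The list there opens with "The following information is then recorded in the eCRF", and its only medication item is "any antidiarrheal medication taken during the current episode". That inference is not supported either. The list mainly describes the present episode and is not an eligibility checklist: atony, cancer and allergy are missing from it too. So is the date of the last menstrual period, which Section 4.2 says will be recorded.

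What the reply leaves untouched is the omission itself. A general criterion relies on someone thinking to ask, a named one prompts the question, and the Protocol names only one of the two contraindications.

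**Conclusion.** The point holds as a minor matter of patient safety and consistency with the label. Section 4.2 names one of the leaflet's two contraindications and leaves the other, in its non-allergic form, to the general suitability judgement. Because eligibility belongs in the protocol, an unseen analysis plan would not fill the gap.

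No probability can be attached to it. The Protocol gives neither the share of patients who have used Enterosgel before nor the share who tolerated it badly. Section 5.2.1 reports use in 30 countries, in some for over 20 years, without reported adverse reactions, so few patients, if any, are likely to be affected. After allocation, the daily calls (Section 6.1.2) and withdrawal on refusal to continue treatment (Section 4.4) limit the harm. Power, sample size and the primary analysis do not change.

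The conclusion assumes that the leaflet in Appendix B is the labelling in force for the trial product, and that exclusion 9 is read by its wording and not stretched to cover past intolerance. If the information sheet or eCRF already asks about earlier use, the practical risk is smaller still, but the exclusion would still be missing from Section 4.2.

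**What to change.** Add an exclusion to Section 4.2: *known intolerance of Enterosgel based on prior use*. Have the nurse or GP ask at the Day 0 eligibility check whether the patient has taken Enterosgel before and, if so, whether it was tolerated.

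The cost is one line of text and one question, through the usual amendment route. The effect on recruitment should be negligible, and no change to the sample size or the analysis is needed.
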